9.4.1 Demographics and Baseline Characteristics

Demography and baseline characteristics (including age, sex, participant disposition, previous therapies and medical history) will be analyzed using descriptive statistics. The analysis will be based on the safety analysis population. Data will be summarized by cohort and regimen within each part.

9.4.2 Efficacy Analyses

The primary and secondary efficacy analyses will include all participants in the efficacy population with participants grouped according to cohort (and schedule if applicable) within each study part. Primary, secondary, and exploratory endpoints are described in Section 3.

The efficacy endpoints of ORR, DCR and PFS according to RECIST v1.1 will be evaluated using the methods described in [Table 22](#):

- Objective response is defined as a CR or PR, as determined by the Investigator's assessment using RECIST v1.1 and confirmed by repeat assessments ≥ 4 weeks after initial documentation. To classify a response as SD, measurements will have to be classified as stable (according to RECIST v1.1) at least once after study entry at a minimum of 6 weeks after study entry.
- ORR and DCR are both determined as the rate of participants with an observed tumor response of CR or PR (ORR) or CR, PR or SD (DCR). ORR and DCR will be derived for RECIST v1.1.
- Among participants with an objective response (responders), DOR will be defined as the time from first occurrence of a documented objective response until the time of documented disease progression or death within 30 days from last study treatment from any cause during treatment, whichever occurs first. Censoring methods will be

the same as the one applied for PFS (on-study drug treatment). This will be calculated for participants who have a best overall response of CR or PR as defined per RECIST v1.1 and per iRECIST.

- PFS (on-treatment) will be defined as the time from study treatment initiation (Cycle 1 Day 1) to the first occurrence of documented disease progression or death from any cause during treatment (death within 30 days from last study treatment), whichever occurs first. For participants who do not have documented progressive disease or death during the study, PFS will be censored at the day of the last tumor assessment. If no post study drug treatment tumor assessment is available, PFS will be censored at the day of the first study drug administration + 1 day.
- OS is defined as the time from the first dose of study treatment to the time of death from any cause on study. Participants who are still alive at the time of analysis will be censored at the time of their last study assessment (for active participants) or at the last date known alive (for participants in follow-up).

Table 22 Efficacy Statistical Analysis Methods

Endpoint	Statistical Analysis Methods

 • ORR • DCR • DOR • PFS (on-treatment) • According to RECIST v1.1 criteria and iRECIST 	
No formal statistical model and no formal hypothesis testing are planned in this study. Tumor response data will be reported using descriptive statistics. Response data will be listed. Participants with missing or no response assessments will be classified as not evaluable unless there is documented clinical deterioration, in which case participants will be classified as non-responders. Reasons for non-evaluability will be summarized (e.g., withdrawal of consent, study discontinuation because of AE or physician decision). ORR and DCR will be summarized by using relative frequencies and 90% confidence interval (CI). Duration of response and PFS (on-treatment) will be summarized by using time-to-event analyses and Kaplan-Meier curves.

 • OS 	
OS data may be tabulated and summarized using time-to-event analyses and Kaplan-Meier curves if data are collected and mature.
 
Summaries will be carried out by cohort (and schedule if applicable) separately for each part. Response data will be listed. This will be carried out for RECIST v1.1 (secondary efficacy endpoints) and iRECIST (exploratory efficacy endpoints).

An exploratory assessment of tumor kinetic modelling may be performed by comparing on-treatment and post-treatment scans with at least two pre-treatment scans not older than 12 weeks prior to Cycle 1 Day 1, if available. For this exploratory assessment, all measurable lesions should be reported. The two pre-treatment scans consist of a pre-study scan and the study baseline scan and will allow estimation of depth and duration of response on target lesion size due to RO7172508 and the effect of

RO7172508 on the risk of the appearance of new lesions during the treatment period. Data will be explored by using linear and/or exponential models, as appropriate, in non-linear mixed effect modeling software, and this exploratory assessment of tumor kinetic modelling will be performed if the data collected allow it.

This will be presented separately from the main clinical study report (CSR).

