6.5.1.1 Radiotherapy

The use of palliative radiotherapy is allowed at any time during the study, **except for:**

- On days when RO7172508 is administered.
- During DLT evaluation period.
 - If radiotherapy is administered during the DLT evaluation period, the participant will not be evaluable.

Participants should not receive study treatment during radiation treatment.

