6.5.2 Prohibited Therapy

All medications (prescription and OTC) taken within 30 days of study screening will be recorded on the appropriate eCRF. As a general rule, no concomitant medication will be permitted, with the exception of medications to treat AEs, unless the rationale for exception is discussed and clearly documented between the Investigator and the Sponsor.

The use of the following therapies is prohibited for at least 28 days prior to initiation of study treatment and during the study, unless otherwise specified below:

- Investigational or unlicensed/unapproved agents
- Immunotherapy/radio-immunotherapy
- Chemotherapy/targeted therapy
- Radiotherapy (with the exception of limited-field palliative radiotherapy; see Section 6.5.1.1).
- Biologic agents (e.g., bevacizumab, erlotinib).
- Chronic use of steroids (inhaled and topical steroids are permitted).
- Administration of a live, attenuated vaccine within 28 days before Cycle 1 Day 1 or anticipation that such a live attenuated vaccine will be required during the study.

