8.1 EFFICACY ASSESSMENTS

8.1.1 Tumor and Response Evaluations

Tumor assessments will be performed at the time-points defined in the SoA (Section 1.3). Tumor response will be evaluated according to RECIST v1.1 ([Appendix 6](#)) using unidimensional measurement such as CT scan or magnetic resonance imaging (MRI). Assessment of CT/MRI scans as tumor assessments will be performed at the sites during the whole study.

The data collected for RECIST v1.1 ([Appendix 6](#)) will be used by the Sponsor to calculate programmatically time-point responses for iRECIST ([Appendix 7](#)), a recently published set of guidelines developed by the RECIST working group in an effort to harmonize immune-based response criteria across the academic and industrial cancer immunotherapy field ([Seymour et al 2017](#)).

Tumor assessment will be performed according to the SoA until disease progression or death. All tumor assessments after baseline may be done within one week of the scheduled visit.

Confirmation of PRs and complete responses (CRs) will be done at the next scheduled visit after at least 28 days from the initial response.

The criteria are needed for continuing treatment beyond RECIST v1.1-defined progression as defined in Section 7.1.

Submission of the latest pre-study or historical CT scans is required for assessment of tumor kinetic modelling within 12 weeks of participant entering the study if available.

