1.1.3 Special Considerations Regarding Lesion Measurability

Bone lesions, cystic lesions, and lesions previously treated with local therapy require particular comment:

Bone lesions:

- *Bone scan, positron emission tomography scan, or plain films are not considered adequate imaging techniques to measure bone lesions. However, these techniques can be used to confirm the presence or disappearance of bone lesions.*
- *Lytic bone lesions or mixed lytic-blastic lesions, with identifiable soft tissue components, that can be evaluated by cross-sectional imaging techniques such as CT or MRI can be considered as measurable lesions if the soft tissue component meets the definition of measurability described above.*
- *Blastic bone lesions are non-measurable.*

Cystic lesions:

- *Lesions that meet the criteria for radiographically defined simple cysts should not be considered as malignant lesions (neither measurable nor non-measurable) because they are, by definition, simple cysts.*
- *'Cystic lesions' thought to represent cystic metastases, can be considered as measurable lesions if they meet the definition of measurability described above. However, if non-cystic lesions are present in the same participant, these are preferred for selection as target lesions.*

Lesions with previous local treatment:

- *Tumor lesions situated in a previously irradiated area, or in an area subjected to other loco-regional therapy, are usually not considered measurable unless there has been demonstrated progression in the lesion. Study protocols should detail the conditions under which such lesions would be considered measurable.*

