Conventional response criteria may not be adequate to characterize the anti-tumor activity of immunotherapeutic agents, which can produce delayed responses that may be preceded by initial apparent radiographic progression, including the appearance of new lesions. Therefore, immunotherapy-specific response criteria adaptations to Response Evaluation Criteria in Solid Tumors, Version 1.1 (RECIST v1.1; Eisenhauer et al. 2009) have been developed to allow for unconventional response and progression patterns. These include modified RECIST v1.1 for immune-based therapeutics (iRECIST; Seymour et al. 2017), which was developed by the RECIST working group in an effort to create a common set of criteria that the cancer immunotherapy field could apply to clinical trials.

Response evaluation through use of iRECIST requires collection of tumor assessment data after radiographic progression per RECIST v1.1. Details regarding lesion evaluation are described below. When not otherwise specified, RECIST v1.1 conventions will apply.

Criteria for determining overall response at a single timepoint per iRECIST are also summarized below. Of note, overall response per iRECIST will not be captured in the electronic Case Report Form (eCRF), but will instead be calculated programmatically by the Sponsor on the basis of investigator-assessed individual lesion data recorded in the eCRF.

iRECIST response status is not a specific component of treatment discontinuation criteria, including decisions about whether to continue treatment beyond progression per RECIST v1.1. Investigators should instead take into account radiologic data and clinical status in making such decisions

EVALUATION OF LESIONS TO SUPPORT iRECIST Response Assessment after Disease Progression per RECIST v1.1

iRECIST is an extension of RECIST v1.1 that allows for response assessment following disease progression per RECIST v1.1. RECIST v1.1 rules for categorizing lesions as measurable or non-measurable and measuring lesions also apply to iRECIST. After disease progression per RECIST v1.1, the same target and non-target lesions selected at baseline will continue to be followed, along with any new lesions that develop, to support iRECIST response evaluations, as described below and summarized in [Table 1](#). Once a lesion has been categorized as a target, non-target, or new lesion, it will remain classified as such.

TARGET LESIONS

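### A target lesion irradiated on study stays in the RECIST sum, so its shrinkage can be scored as a response to RO7172508

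*Combined protocol and SAP*

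**What the plan says.** Section 6.5.1.1: "The use of palliative radiotherapy is allowed at any time during the study", except on RO7172508 dosing days and in the DLT period. The only analysis consequence given there is "If radiotherapy is administered during the DLT evaluation period, the participant will not be evaluable". That window is about 3 to 8 weeks depending on study part and schedule, within a treatment period of up to 24 months.

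Section 9.4.2: "ORR and DCR are both determined as the rate of participants with an observed tumor response of CR or PR (ORR", and DCR adds SD. Response is by Investigator assessment under RECIST v1.1 and must be confirmed at least 4 weeks later. Without progression or death, "PFS will be censored at the day of the last tumor assessment", and DOR uses the same censoring. Neither this section nor Table 22 mentions radiotherapy.

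Appendix 6, Section 1.1.3: "Tumor lesions situated in a previously irradiated area, or in an area subjected to other loco-regional therapy, are usually not considered measurable" unless progression in the lesion has been shown. This stands under measurability at baseline. The appendix leaves the detail to the protocol, which gives none.

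Appendix 6, Sections 2.3.1 and 2.3.2: PR is a fall of at least 30% in the target sum from baseline, and lesions recorded at baseline have their actual size entered at every later evaluation. Section 2.4.2 reserves not-evaluable status for lesions that were not imaged or could not be read.

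Sections 4.1 and 4.1.2.2: a PR or better under IV dosing is one of the conditions that allow SC cohorts to open.

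**The concern.** Radiotherapy to a target lesion can shrink it whether or not RO7172508 works. The plan allows the radiotherapy, keeps the lesion in the sum, and counts the resulting fall. Confirmation gives no protection, because shrinkage after radiotherapy can still be there at the next scan.

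At stake are the secondary activity endpoints, the response condition for SC cohorts, and the activity evidence that Section 4.1.2.2 uses when the OBD is chosen. With at least 3 evaluable participants per cohort, one misattributed response changes how a dose level reads. If no rule is set beforehand, someone will have to decide case by case, in an open-label study, whether a particular response counts.

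**Working it through.** The plan states no figure for this point, so there is none to reproduce. The check applies the written rules to an example and then sizes one misattributed response.

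**1. Inputs from the documents.** PR: at least a 30% fall in the target sum from baseline. PD: at least a 20% rise, and at least 5 mm, over the smallest sum on study (both Appendix 6, Section 2.3.1). Targets: up to five, at most two per organ (Appendix 6, Section 2.2). Scans: before Cycle 3, every 6 weeks for 12 weeks, then every 12 weeks (schedules of activities).

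**2. Example (lesion sizes assumed).** Two targets of 40 mm, sum 80 mm. One is irradiated after Cycle 2 and falls to 12 mm; the other is unchanged.
- New sum = 12 + 40 = 52 mm.
- Change = (52 − 80)/80 = −35%, past the PR threshold.
- If the next scan agrees, this is a confirmed PR under Section 9.4.2, with no drug effect.

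**3. General condition.** If the irradiated lesions make up a share f of the baseline sum and shrink by a fraction s, and the others are stable (assumption), a PR needs f × s ≥ 0.30.

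| Share f of baseline sum | Shrinkage s needed = 0.30/f |
|---|---|
| 100% | 30% |
| 60% | 50% |
| 50% | 60% |
| 40% | 75% |
| 30% | 100% |

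**4. Progression and PFS, same example.** Against a smallest sum of 80 mm, PD on the targets needs 1.20 × 80 = 96 mm.
- First lesion still 40 mm: the other must reach 96 − 40 = 56 mm.
- First lesion irradiated to 12 mm: the other must reach 96 − 12 = 84 mm, so growth is masked.
- Once 52 mm has been recorded as the smallest sum, PD needs 1.20 × 52 = 62.4 mm, so the other lesion need only reach 62.4 − 12 = 50.4 mm, and PD is called sooner.

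PFS can therefore shift in either direction. New lesions or unequivocal non-target progression still count as PD throughout.

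**5. Effect of one such PR on ORR.** The plan asks for 90% intervals without naming a method; Clopper-Pearson is assumed.

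| Group | Without it | With it | Shift |
|---|---|---|---|
| 3 | 0/3 (0–63%) | 1/3 = 33% (2–86%) | 33 points |
| 6 | 0/6 (0–39%) | 1/6 = 17% (1–58%) | 17 points |
| 15 | 0/15 (0–18%) | 1/15 = 6.7% (0.3–28%) | 6.7 points |

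**6. How often.** The documents give no rate. If a proportion q of participants had such a response, the chance of at least one among n is 1 − (1 − q)^n. For assumed q of 2%, 5% and 10% this is 26%, 54% and 79% with n = 15, and 70%, 95% and 99.8% with n = 60.

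Simulation does not settle q. Assume no drug effect, the largest target irradiated after week 6, 3% growth per 6 weeks in the others, 8% measurement error, and PR required at weeks 12 and 18. With 50% mean shrinkage, a confirmed PR follows irradiation in 87%, 35% and 9% of participants with 1, 2 and 3 targets; with 70% shrinkage, in 99%, 76% and 35%. With 30% shrinkage the figures are about 38%, 7% and 1%. With 50% shrinkage but 10% growth and a 20% chance per interval of progression elsewhere, they are about 32%, 7% and 1%. A spread from about 1% to 99% shows that the assumptions drive the answer.

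**The case against.** **The plan is silent; it does not instruct anyone to count these lesions.** Response is the Investigator's call, and an Investigator might set an irradiated lesion aside. This holds to the extent that the shrinkage can be credited, not that it always will be. But Appendix 6 does require the actual measurement of baseline lesions at later evaluations, and no not-evaluable category fits a lesion that is imaged and readable. Followed as written, it yields a PR.

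**Appendix 7 seems to settle it.** A reader might cite "Once a lesion has been categorized as a target, non-target, or new lesion, it will remain classified as such" as proof that irradiated targets are kept in ORR. That sentence belongs to iRECIST, concerns lesions followed after RECIST v1.1 progression, and serves an exploratory endpoint. It does not bear on v1.1 ORR; the point rests on Appendix 6.

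**Later systemic therapy.** From "Tumor assessment will be performed according to the SoA until disease progression or death" a reader might infer that responses to a new systemic treatment are also counted. The documents do not support this. Such therapies are "prohibited for at least 28 days prior to initiation of study treatment and during the study" (Section 6.5.2), PFS is labelled on-treatment, and the tumor-assessment rows of the schedules (Tables 1, 2, 3 and 7) stop at End of Treatment. Only an ambiguity about how long scans run is left. Censoring at new therapy would also be an estimand choice, not the repair of an error.

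**Little depends on efficacy.** It is secondary and descriptive, with no testing. Section 9.4 does not expect it to be a key criterion for choosing the route. A PR only permits SC cohorts, MTD is an alternative trigger, and the SC starting dose is limited by IV experience. Responses are listed individually. All of this stands and limits the consequences. It does not correct the reported ORR, nor say whether a PR after irradiation satisfies the trigger.

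**Conclusion.** The concern holds for radiotherapy. Under the response rules as written, shrinkage of a target lesion irradiated on study can count as a CR or PR in ORR, as disease control in DCR, and as the start of a response in DOR. It can move PFS either way and can meet the response condition for opening SC cohorts.

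The size per event is firm: 33 points of ORR in a cohort of 3, and 17 points in one of 6. The frequency is unknown. The documents give no rate of target irradiation, no shrinkage after it and no growth rate, so no overall bias in ORR can be stated, and the simulated percentages above are illustrations only.

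**What to change.** Add to Section 9.4.2:

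- From the date a target lesion is irradiated, later time-points are not evaluable for CR, PR or SD. Progression still counts.
- A response counts in ORR, or towards the SC trigger in Sections 4.1 and 4.1.2.2, only if documented and confirmed before that date.
- DOR and PFS are also shown, as a sensitivity analysis, censored at the last scan before irradiation.

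Record the anatomical site and date of on-study radiotherapy, so that it can be matched to target lesions. Section 6.5.1 asks for dates of medications but does not mention irradiation site.

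The cost is a few sentences, one data field and a derivation flag; what radiotherapy is permitted does not change. The downside is that a few responses become not evaluable, including some genuine ones. An unconfirmed PR at the time of irradiation would follow the existing PR-then-NE row of Table 3 in Appendix 6.

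Separately, as a minor point: reconcile the scan duration in Section 8.1.1 with the schedules that end tumor assessment at End of Treatment, and state the on-treatment window for scans, since the 30-day limit in Section 9.4.2 is attached to deaths only.

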- 12-lead ECG at screening (within one week before first dose of RO7172508). After Cycle 4, 12-lead ECG to be done only at every second cycle (i.e. Cycle 6, Cycle 8 etc.). Additional unscheduled ECG assessments in triplicate should be performed in case of abnormalities and if clinical symptoms occur. Recording must be done prior to PK sampling.

Table 2 Part II: Multiple Participant Cohorts IV Q3W/Multiple Ascending Dose-Escalation (cont.)

- e) Serum pregnancy test at screening, within 7 days prior to first dose, and at the safety follow-up visit; a urine pregnancy test will be performed at specified subsequent visits. If a urine pregnancy test is positive, it must be confirmed by a blood pregnancy test. Results must be obtained and reviewed prior to administration of RO7172508.
- f) Hematology, blood chemistry, coagulation, and urinalysis can be performed within 24 hours (up to 72 hours if during weekend) prior to scheduled dosing. Screening results can be within 1 week prior to C1D1. Results must be obtained and reviewed prior to administration of RO7172508.
- g) Tumor biopsy samples will be collected during screening, once during the study treatment period at Cycle 2 Day 8 and optionally at the end of treatment visit ONLY if the reason for discontinuation is progressive disease. If a fresh biopsy is performed for screening purposes, this can be used as the baseline sample.
- h) As part of the eligibility procedure, CEA expression will be confirmed on archival tumor material, *with the exception of CRC participants*. If no archival tumor sample is available, fresh sample will be collected and be assessed (the same sample would constitute as baseline screening sample if participant is enrolled). Archival tissue should be submitted for additional biomarker assessments for all participants (if available).
- i) Tumor response is assessed by the Investigator per RECIST V1.1 with the use of physical examination and image-based evaluation. All measurable and evaluable lesions should be assessed and documented during the screening period, within 7 days before Cycle 3 Day 1, thereafter every 6 weeks (± 7 days) for 12 weeks, and then every 12 weeks (± 7 days) until disease progression or death. (i.e. screening, C3, C5, C7, C11, C15, C19 etc.).
- j) All planned assessments are to be performed before administration of RO7172508. At least 24 hours (overnight) hospital stay required following administration of study drug at Cycle 1 Day 1.

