- k) TCR $V\beta$ and CtDNA/tumor marker samples to be drawn at Cycle 1 Day 1 predose (baseline) and Cycle 5 Day 1 predose.
- l) To allow estimation of tumor growth rate before start of treatment, an exploratory assessment of tumor kinetics will be made by comparing post-treatment scans with at least 2 pretreatment scans not older than 12 weeks prior to C1D1, if available. One of the pretreatment scans will be the study baseline scan taken during screening and the second will be within the preceding 12 weeks.
- m) Cytokines from Cycle 5 onwards, samples to be taken every second cycle up to Cycle 15 (e.g. C5, C7 etc.).
- n) RBR (RNA) and CtDNA/tumor markers samples to be taken on Cycle 5 only.
- o) Sample to be taken only if \geq Grade 2 the safety event is suspected to be immune-related (e.g., IRR). Refer to [Table 5](#) for additional assessments if safety event is an IRR/CRS (\geq Grade 3) that requires tocilizumab treatment. *Any biopsy samples or results done as part of standard of care can be shared with the Sponsor if applicable.*
- p) The Day 3 visit may be adjusted ± 1 day depending on safety and PD data. The visit optimal timepoint will be communicated to the Investigators for consistency and should occur ± 4 hrs from each complete day of administration (i.e. 24hrs ± 4 hrs; 48 hrs ± 4 hrs; OR 72hrs ± 4 hrs).
- q) Survival follow-up visit to be performed 90 days (± 7 Days) after the last treatment either in person or a phone call to document any ongoing or resolved AEs, and every 3 months (± 2 weeks) thereafter for overall survival.

Table 2 Part II: Multiple Participant Cohorts IV Q3W/Multiple Ascending Dose-Escalation (cont.)

- r) Serology (as per local regulations) includes HIV, hepatitis B surface antigen, total hepatitis B core antibody, hepatitis C virus antibody. Results must be obtained and reviewed prior to administration of RO7172508.
- s) Weight to be recorded pre-infusion. Height to be measured at screening only.
- t) Required for Cycle 5 only.
- u) Samples to be collected only in Cycle 1
- v) Vital signs include systolic and diastolic blood pressure; pulse rate; temperature; respiratory rate and oxygen saturation.
- w) Pulmonary function tests should include spirometry; forced expiratory volume (FEV1), forced vital capacity (FVC) and Diffusion capacity (DLCO).
- x) Refer to [Table 6](#) in the event obinutuzumab pre-treatment is implemented for specific additional assessments during the screening period.

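### On-treatment PFS and DOR exclude deaths more than 30 days after the last dose, which biases PFS upward and can lengthen DOR, and Section 9.4.2 does not code those deaths unambiguously

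*Combined protocol and SAP*

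**What the plan says.** All the relevant rules are in Section 9.4.2.

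- **PFS event:** progression, or "death from any cause during treatment (death within 30 days from last study treatment".
- **DOR event:** "documented disease progression or death within 30 days from last study treatment from any cause during treatment".
- **PFS censoring:** for participants without "documented progressive disease or death during the study, PFS will be censored at the day of the last tumor assessment".
- **PFS with no post-dose scan:** "PFS will be censored at the day of the first study drug administration + 1 day".
- **DOR censoring:** "the same as the one applied for PFS (on-study drug treatment".
- **DOR population:** responders only, with the response "confirmed by repeat assessments ≥ 4 weeks after initial documentation".

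The schedules in Section 1.3 place the first post-baseline scan "within 7 days before Cycle 3 Day 1, thereafter every 6 weeks". Table 8 lists PFS, labelled on-treatment, and DOR as secondary endpoints for preliminary activity. Table 22 plans descriptive Kaplan-Meier summaries by cohort, with no hypothesis test. OS is exploratory and counts death from any cause, but Table 22 makes its summary optional and dependent on data maturity.

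**The concern.** Kaplan-Meier censoring assumes that those censored have the same outlook as those still at risk. A participant who stops for toxicity or clinical decline and dies after the 30-day window probably had a worse outlook. Removing that death leaves a healthier risk set and raises the PFS curve. For a responder who dies after the window without progression, DOR is censored instead of ending at death.

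The plan is also uneven. For response, Table 22 classes an unassessed participant with documented clinical deterioration as a non-responder. For PFS, the same participant becomes a censored observation if death falls outside the window. Appendix 6 (Section 2.4.3) does not accept symptomatic deterioration as an objective response category, so decline without a scan is not a progression event either.

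At stake is the description of preliminary activity. No formal test depends on it.

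**Working it through.** The documents give no event count or expected value for PFS or DOR, so there is no planned figure to reproduce. The check has three steps.

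**1. Apply the PFS rules to example dates.** With 21-day cycles, doses fall on Days 1, 22, 43 and 64. Cycle 3 Day 1 is 1 + 2×21 = Day 43, so the first scan is due about Day 36 to 43. A death counts through last dose + 30: Day 31 after one dose (1 + 30) and Day 52 after two (22 + 30). No progression is assumed in any row.

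| Last dose | Post-dose scans | Death | Coding on the natural reading |
|---|---|---|---|
| Day 1 | none | Day 15 | event, Day 15 |
| Day 1 | none | Day 31 | event, Day 31 |
| Day 1 | none | Day 32 | censored, Day 2 |
| Day 22 | none | Day 45 | event, Day 45 |
| Day 22 | none | Day 53 | censored, Day 2 |
| Day 64 | Days 40, 82 | Day 110 | censored, Day 82 |

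The deaths lost are those well after stopping, not those soon after dosing. The Day 2 rule cannot reach DOR, because every confirmed responder has post-dose scans.

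**2. Set the two phrases side by side.** Take one dose on Day 1, no scan, and death on Day 45. That is 44 days after dosing, so it fails the event definition, which is tied to treatment. The participant has nevertheless died on study, and the censoring sentence covers only those with neither progression nor death on study. Read literally, the participant belongs to neither group. Censoring is the natural inference, but the text does not state it.

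**3. Size the unscanned route.** Let q be the fraction never scanned after dosing who die more than 30 days after the last dose, and let S_rest(t) be the event-free proportion in everyone else. Under the plan the q group leaves at Day 2, so S_plan(t) = S_rest(t). If all deaths count, then once the q group has died S_all(t) = (1−q)·S_rest(t). Hence S_plan/S_all = 1/(1−q):

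- q = 5%: 1/0.95 = 1.05
- q = 10%: 1/0.90 = 1.11
- q = 20%: 1/0.80 = 1.25

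A simulation checked this with 20,000 participants per setting. It assumed exponential times with a 90-day median for the others and unscanned deaths uniform over Days 32 to 75.

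| Assumed q | 90-day event-free: plan / all deaths | Median in days: plan / all deaths |
|---|---|---|
| 0% | 0.503 / 0.503 | 91 / 91 |
| 5% | 0.501 / 0.475 | 91 / 84 |
| 10% | 0.506 / 0.453 | 92 / 77 |
| 20% | 0.503 / 0.403 | 91 / 69 |

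Medians of 60 and 120 days gave nearly the same 90-day ratios (1.05, 1.11, and 1.25 to 1.26). The formula does not cover participants censored at a later scan, as in the last row of the first table. That route works in the same direction but was not sized.

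**The case against.** The strongest reply is that the endpoint does what its label says. It is called on-treatment wherever it is listed, it is descriptive, and Section 9.4 says efficacy is not expected to be a key criterion for choosing the route of administration. OS keeps the later deaths, and Section 9.4.3 provides listings of deaths.

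The schedule also narrows the affected group. Participants who stop prematurely are asked back for an end-of-treatment visit (Section 7.1), set at 28 days after the last dose (Section 8.10.3), and the schedules list a tumor assessment there. After a single dose that is Day 29, before the 30-day window closes. Section 8.1.1 continues scans until progression or death, and Section 8.1.1.1 asks for full imaging when progression is suspected. Being never scanned and dying outside the window therefore mostly requires missed visits.

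Much of this stands and limits the size. It does not dispose of the point: an end-of-treatment scan without progression moves the censoring date but does not make the later death an event, OS is optional and does not replace PFS or DOR, and the label does not resolve the conflicting wording.

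Some stronger readings are tempting but unsupported. A reader might infer that early deaths in general drop out; any death within 30 days of the last dose is an event, scanned or not. A reader might infer that the Day 2 rule distorts DOR; it cannot. A reader might also attach a large inflation to the first scan. By Day 36 to 43 on three-weekly dosing, only one-dose participants dying from Day 32 onward could be affected, eligibility requires a life expectancy of at least 12 weeks, and no document gives their frequency.

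**Conclusion.** The point holds as a minor one. Excluding deaths beyond 30 days after the last dose biases PFS upward and can overstate DOR, provided stopping is related to prognosis and the deaths are censored as the event definition implies. The text itself does not settle that coding.

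The size cannot be taken from the documents. The factors 1.05, 1.11 and 1.25 rest on assumed q of 5%, 10% and 20%, apply to PFS only after those deaths have occurred, and should be read as a scale rather than a forecast. In cohorts that may have three participants, counts matter more than percentages: one such participant gives q = 1/3 and a factor of 1/(1 − 1/3) = 1.5. Nothing in the documents suggests that a dose or route decision would change.

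**What to change.** 1. In Section 9.4.2, reconcile the treatment-based event wording with the study-based censoring wording, and state how a death more than 30 days after the last dose without progression is coded for PFS and for DOR.
2. Add to Section 9.4.2 and Table 22 a supplementary PFS and DOR in which progression or death from any cause on study is an event, shown beside the on-treatment version.
3. Report per cohort the number of deaths excluded by the 30-day rule and the number of PFS times censored on the day after first dose.

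No new data are needed. Scans already run until progression or death, and the survival follow-up footnotes in Section 1.3 provide a contact at 90 days ("either in person or a phone call to document any ongoing or resolved AEs") and then every three months for overall survival. The cost is one extra Kaplan-Meier summary per cohort, and the supplementary PFS may look slightly less favourable.
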